4.1.2 Number of Study Sites

The study will be performed at the primary site, Hackensack University Medical Center, and up to 50 additional subsites in the USA currently implanting Impulse Dynamics Optimizer devices per standard of care.

4.2 Study Population

The population will include adult patients, at least 18 years of age.

1. Retrospective study
 - a. CIED with the ability to interpret atrial signals implanted at least 6 months prior to Optimizer implantation AND Optimizer implantation at least 6 months post CIED implantation and with at least 8 months of post Optimizer implantation follow up.
 - b. OR if the patient has an appropriate CIED with at least 6 months of follow up prior to Optimizer implantation, but less than 8 months of follow up after Optimizer implantation (will require a signed informed consent form).
2. Prospective study

CIED with the ability to interpret atrial signals implanted at least 6 months prior to CCM implantation AND scheduled CCM implant which was prescribed for standard clinical indications.

4.2.1 Number of Participants

We would like to evaluate up to 200 subjects from up to 50 subsites.

4.2.2 Eligibility Criteria

The population will include subjects with the following for the:

1. Retrospective arm
 - a. Optimizer implantation at least 6 months post CIED implantation and with at least 8 months of post Optimizer implantation follow up
 - b. Patient has an appropriate CIED with at least 6 months of follow up prior to Optimizer implantation, but less than 8 months of follow up after Optimizer implantation (will require a signed informed consent form).

| | |
|--------------|------------|
| Study Number | 12/20/2022 |
|--------------|------------|

2. Prospective arm
 - a. CIED with the ability to interpret atrial signals implanted at least 6 months prior to Optimizer implantation;
 - b. Scheduled Optimizer implant which was prescribed for standard clinical indications.

4.2.3 Inclusion Criteria

1. $1\% \leq \text{AF burden} \leq 99\%$ in the 6 month period prior to Optimizer implant as documented the patient's CIED
2. 18 years of age or older on day of signing consent
3. Any gender
4. Functional dual chamber pacemaker or ICD and using remote follow up for their CIED
5. Not scheduled for planned catheter ablation or cardioversion
6. Ability to sign consent in English or Spanish

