CLINICAL STUDY PROTOCOL

Arrhythmia Burden in Patients with Impulse Dynamics Optimizer Smart Device Implantation: Retrospective and Prospective Evaluation

Protocol Version
12/23/2022

version 1.0

| | |
|--------------|------------|
| Study Number | 12/20/2022 |
|--------------|------------|

Study Authors

[name]

Lead Study Principal Investigator: [name]

Hackensack University Medical Center,

Hackensack Meridian School of Medicine

Abbreviations

| Abbreviation | Explanation |
|--------------|-------------|
|--------------|-------------|

AF=Atrial fibrillation

CCM= Cardiac Contractility Modulation

CHF=congestive heart failure

CIED= cardiovascular implantable electronic device

FDA=Food and Drug Administration

HFrEF=heart failure with reduced ejection fraction

ICD=Internal Cardioverter Defibrillator

ILR=implantable loop recorder

PPM=Permanent pacemaker

LVEF=left ventricular ejection fraction

NYHA>New York Heart Association

VA=Ventricular arrhythmia

VF=Ventricular fibrillation

VT=Ventricular tachycardia

| | |
|--------------|------------|
| Study Number | 12/20/2022 |
|--------------|------------|

Summary

The Impulse Dynamics Optimizer Device is a Food and Drug Administration (FDA) approved, commercially available device indicated for patients with heart failure with reduced ejection fraction (HFrEF), currently being implanted per FDA recommendation. Many candidates of this device have a previously implanted cardiovascular implantable electronic device (CIED)- internal cardioverter defibrillator (ICD) or permanent pacemaker (PM). Patients with heart failure are at high risk for both atrial and ventricular cardiac arrhythmias.

The aim of this study is to evaluate up to 200 patients for Atrial fibrillation (AF) burden episode data obtained from interrogation of their CIED 8 months or greater after Optimizer implant, and compare arrhythmia burden 6 months before Optimizer Cardiac Contractility Modulation (CCM) device insertion to 6 months or greater after Optimizer insertion, after an immediate implantation blanking period of 2 months.

| | |
|--------------|------------|
| Study Number | 12/20/2022 |
|--------------|------------|

1 – Introduction

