3.4.2 Exploratory Objective Two

Exploratory objective two is to compare the number of VA episodes between all groups noted above.

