In terms of arrhythmia reporting, AF burden will be reported as (1) hours of AF/day (2) percent AF per day and (3) number of AF episodes \geq 24 hours/1 month period, including in the 2 month blanking period.

VA episodes will be categorized into types and number of events as reported by the CIED as (1) treated VT and treated VF together and (2) untreated non-sustained VT, treated VT, and treated VF together.

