4.3 Study procedures

AF burden and VT episodes will be remotely accessed from the CIED manufacturer. The prospective arm will allow prospective data collection for 8 months after Optimizer implantation, including a 2 month blanking period immediately after Optimizer implantation.

For the retrospective and the prospective arms, the data will be evaluated in the same manner, except as noted below, and will be performed as follows:

1. Pre-6 months to Optimizer implant (will be subcategorized into pre-6 to pre-3 months, and pre-3 months to Optimizer implant), to ensure $1\% \leq \text{AF burden} \leq 99\%$ (otherwise subjects will be excluded).
2. Optimizer implant date will be followed by a 60 day blanking period. The patients will be followed for 8 months [will be subcategorized into Optimizer implant to post-2 months (blanking period), post-2 month blanking period to post-5 months, and post-5 months to post-8 months, and every 3 months thereafter until the study is completed).

AF burden will be reported as (1) hours of AF/day (2) percent AF per day and (3) number of AF episodes ≥ 24 hours/1 month period, including the blanking period.

Demographics, development of medical events (hospitalization, stroke) and arrhythmia related history (presence/absence of medications) and interventions, such as cardioversion, antiarrhythmic drug administration, or catheter ablation will be recorded.

VA episodes will be categorized into types and number of events as reported by the CIED as (1) treated VT and treated VF together and (2) untreated non-sustained VT, treated VT, and treated VF together.

| | |
|--------------|------------|
| Study Number | 12/20/2022 |
|--------------|------------|

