5.2 Analysis Population

All patients identified and enrolled will be included in the analyses.

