A patient's AF burden is measured as the cumulative time spent in AF over the assessment period divided by the cumulative follow-up time of the assessment period. The difference in AF burden between the post-Optimizer and pre-Optimizer AF assessment periods will be analyzed as a continuous variable. Visual inspection of q-q plots for skewness and outliers along with the Shapiro-Wilk test ($p>0.05$ indicates no deviation from normality and $p<0.05$ indicates deviation from normality) will be used to evaluate normality. If the distribution of changes in AF burden is approximately normally distributed, a paired t-test will be used for analysis and the mean, standard deviation, and range will be reported. Otherwise, if the distribution is non-normal, a Wilcoxon signed-rank test will be performed and the median, interquartile range, and range will be reported.

VA episode counts will be tabulated for the pre-Optimizer and post-Optimizer assessment periods. A Poisson generalized estimating equation (GEE) analysis accounting for clustering of paired counts within subject may be performed to compare the rate of VA episodes between the pre-Optimizer and post-Optimizer assessment periods.

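### Pacemaker-only patients enter the treated VT/VF counts as fixed zeros: per-patient rates are understated, and the pre/post ratio is affected only if device type changes

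*Combined protocol and SAP*

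**What the plan says.** The protocol's Summary describes a CIED as an "internal cardioverter defibrillator (ICD) or permanent pacemaker (PM"), and inclusion criterion 4 in section 4.2.3 accepts either: "Functional dual chamber pacemaker or ICD and using remote follow up for their CIED". The other device requirements (sections 4.1, 4.2 and 4.2.2) are that it can read atrial signals and has been in place for six months before the Optimizer.

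Section 3.4.2 sets the ventricular objective: "Exploratory objective two is to compare the number of VA episodes between all groups noted above". The counts come from the device. Section 4.3 states "VA episodes will be categorized into types and number of events as reported by the CIED", in two categories: ("1) treated VT and treated VF together and (2) untreated non-sustained VT, treated VT, and treated VF together".

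Section 5.2 reads "All patients identified and enrolled will be included in the analyses". Section 5.3.2 adds "VA episode counts will be tabulated for the pre-Optimizer and post-Optimizer assessment periods", followed by a Poisson GEE on paired counts that is optional. It names no ICD subset, no stratification by device type and no rule for a patient whose device changes. CIED type is not among the descriptive variables in section 5.3 or the recorded items in section 4.3.

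**The concern.** Either device can supply AF burden, so criterion 4 suits the primary objective. It does not suit the first VA category. That category needs a device that can treat VT or VF, and a pacemaker without defibrillator function cannot. Such a patient contributes a structural zero in both windows.

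Two separate things are at stake. The first is interpretation of the level: a treated-VA rate per enrolled patient would mix patients at risk of the outcome with patients who cannot have it. Section 5.3.2 reports by arm and combined, so a different device mix in the two arms would by itself make their rates differ. The second is a possible artefact in the comparison: a patient who goes from pacemaker to ICD between the windows has a pre-Optimizer count fixed at zero and a post-Optimizer count that can be zero or more. Section 5.4 runs the same methods after every 25 patients and section 6.6 allows interim results to be published, so a few such patients could weigh visibly in a small table.

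**Working it through.** **The plan's own figure.** The documents give no VA rate, VA power or device mix. The only sample-size figure, 77 in section 5.1, concerns AF burden. It reproduces: a two-sided paired t-test with mean change 5, SD 15, alpha 0.05 and power 0.8 needs 73, and 73 × π/3 = 76.4, rounded up to 77. Nothing below depends on it. The planned maximum of 92 per arm, also from section 5.1, is used only as a denominator.

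**Assumed inputs.** f = share of subjects with a pacemaker only before the Optimizer (10%, 25%, 50%). u = share of those subjects who change to an ICD between the windows (10%, 25%).

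**Step 1, level.** With no device changes, all-patient rate = (1 − f) × ICD-only rate. The absolute pre/post difference scales by the same factor.

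| f | Rate relative to ICD-only | Patients per arm who can have a treated event |
|---|---|---|
| 10% | 0.90 | 92 × 0.90 = 82.8 |
| 25% | 0.75 | 92 × 0.75 = 69 |
| 50% | 0.50 | 92 × 0.50 = 46 |

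The raw total of events does not change; only quantities divided by all enrolled patients do.

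**Step 2, ratio.** The factor cancels: (1 − f) × post ÷ [(1 − f) × pre] = post ÷ pre. As a check, a Poisson GEE was fitted to one simulated set of 92 ICD patients, then refitted after adding zero-count pacemaker patients.

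| f | Total patients | Pre rate | Post rate | Difference | Rate ratio | SE(log) | p |
|---|---|---|---|---|---|---|---|
| 0 | 92 | 1.022 | 0.891 | −0.130 | 0.872 | 0.132 | 0.30 |
| 10% | 102 | 0.922 | 0.804 | −0.118 | 0.872 | 0.132 | 0.30 |
| 25% | 123 | 0.764 | 0.667 | −0.098 | 0.872 | 0.132 | 0.30 |
| 50% | 184 | 0.511 | 0.446 | −0.065 | 0.872 | 0.132 | 0.30 |

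The rates and difference shrink; the ratio, its standard error and its p-value do not move.

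**Step 3, device change.** Suppose there is no true effect, all changes fall between the windows, and changed patients have the same treated-VA rate as established ICD patients. Then the apparent ratio = [(1 − f) + f × u] ÷ (1 − f).

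| f | u = 10% | u = 25% |
|---|---|---|
| 10% | 0.91/0.90 = 1.01 | 0.925/0.90 = 1.03 |
| 25% | 0.775/0.75 = 1.03 | 0.8125/0.75 = 1.08 |
| 50% | 0.55/0.50 = 1.10 | 0.625/0.50 = 1.25 |

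In patients who already had an ICD at the start of the pre-Optimizer window, the ratio under the same assumptions is 1.00.

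**Step 4, the second category.** It adds untreated non-sustained VT, which a pacemaker may report. A sustained VT that is recorded but not treated fits neither category, so the second category also has a different meaning in pacemaker patients.

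**The case against.** The best reply is that the only comparison planned for VA is a paired, within-patient ratio, which step 2 shows is untouched by constant zeros. That is right. A reader might infer that pacemaker patients pull the GEE towards no effect or cost it precision; they do neither.

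A second reply is that device changes are speculative. The eligibility text speaks of one established CIED per patient, at least six months old, and never describes a change. This stands in part: the artefact is conditional. But no section excludes or handles a change after enrolment, so a rule is still needed. A reader might also infer that the plan has a built-in signal of harm, or a large one. The documents do not support that. An apparent ratio of 1.40, for example, needs half the cohort to start with a pacemaker and 40% of those to change: (0.50 + 0.50 × 0.40)/0.50 = 1.40. Nothing in the text suggests such numbers.

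Third, VA is one of nine exploratory objectives, has no power calculation, and its test is optional. Section 5.2 need not forbid subsets, since objectives three and four already set subjects aside. This limits the weight of the point. It does not supply the missing subset: objectives three and four state their restrictions, and objective two states none.

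**Conclusion.** The point holds in a limited form. Followed as written, the plan puts pacemaker-only patients into a treated VT/VF table in which they cannot have an event. Per-patient rates and absolute differences are then understated by exactly the pacemaker share, 10% to 50% over the range assumed. The pre/post rate ratio and its test are sound as long as device type stays constant. If 10% to 25% of pacemaker patients move to an ICD between the windows, the ratio under no effect is about 1.01 to 1.25, always in the direction of more treated VA after the Optimizer.

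The conclusion that rates are diluted needs only that some pacemaker patients enrol. The sizes rest on assumed shares, and the ratio range also on the timing and equal-rate assumptions in step 3. The AF-burden primary analysis is not affected. This is an inexpensive correction to an exploratory analysis and does not threaten the study's main result.

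**What to change.** Keep criterion 4 as it is for AF burden, and make these changes:

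- **Data (section 4.3):** record CIED type with dates, and add it to the descriptive variables in section 5.3.
- **First VA category (section 5.3.2):** restrict the treated VT/VF comparison to subjects whose CIED was already an ICD at the start of the pre-Optimizer window, and state that ICD denominator.
- **Second VA category:** report it separately for ICD and pacemaker subjects.
- **Device changes:** list subjects who change device type separately, with their VA counts. Keep them in every analysis that does not depend on device therapy: AF burden, hospitalization, stroke, ablation and cardioversion.

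The subset should be defined at the start of the pre-Optimizer window. Requiring an ICD throughout both windows would select on a post-implant event. If a ventricular arrhythmia prompted the device change, dropping that patient would remove an informative case and could hide a real increase.

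The cost is one dated field and a few lines of text. The downside is fewer subjects in the exploratory treated-VA table. Removing those with a pacemaker throughout loses no treated events, and any events in subjects who change device remain visible in the separate listing.

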4.2.4 Exclusion criteria

1. Permanent atrial fibrillation
2. Pregnancy (in prospective arm only)
3. Expected survival <1 year

4.3 Study procedures

AF burden and VT episodes will be remotely accessed from the CIED manufacturer. The prospective arm will allow prospective data collection for 8 months after Optimizer implantation, including a 2 month blanking period immediately after Optimizer implantation.

For the retrospective and the prospective arms, the data will be evaluated in the same manner, except as noted below, and will be performed as follows:

1. Pre-6 months to Optimizer implant (will be subcategorized into pre-6 to pre-3 months, and pre-3 months to Optimizer implant), to ensure $1\% \leq \text{AF burden} \leq 99\%$ (otherwise subjects will be excluded).
2. Optimizer implant date will be followed by a 60 day blanking period. The patients will be followed for 8 months [will be subcategorized into Optimizer implant to post-2 months (blanking period), post-2 month blanking period to post-5 months, and post-5 months to post-8 months, and every 3 months thereafter until the study is completed).

AF burden will be reported as (1) hours of AF/day (2) percent AF per day and (3) number of AF episodes ≥ 24 hours/1 month period, including the blanking period.

Demographics, development of medical events (hospitalization, stroke) and arrhythmia related history (presence/absence of medications) and interventions, such as cardioversion, antiarrhythmic drug administration, or catheter ablation will be recorded.

VA episodes will be categorized into types and number of events as reported by the CIED as (1) treated VT and treated VF together and (2) untreated non-sustained VT, treated VT, and treated VF together.

| | |
|--------------|------------|
| Study Number | 12/20/2022 |
|--------------|------------|

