The Impulse Dynamics Optimizer is indicated for patients with New York Heart Association (NYHA) class III congestive heart failure (CHF) with left ventricular ejection fraction (LVEF) between 25 and 45% who are not candidates for cardiac resynchronization therapy. The Optimizer device requires a minimally invasive implant by a cardiac electrophysiologist with two transvenous pacemaker wires implanted into the right ventricular septum and attached to a generator in an infraclavicular region, much like a pacemaker. The Optimizer device provides CCM through improved calcium handling and has been shown to reverse the negative remodeling of the left ventricle seen in HFrEF and improve left ventricular contractile strength.

We plan to enroll a maximum of 200 patients with existing or newly implanted Impulse Dynamics Optimizer with concurrent previously implanted CIED.

2 – Background

AF demonstrates an average prevalence of 25% in HFrEF, and is the most common sustained arrhythmia encountered in the HFrEF population (1). AF burden in HFrEF is estimated at 35%. AF increases risks of CHF hospitalizations and mortality in HFrEF (2). Episodes of AF longer than 24 hours in a non HFrEF population substantially increased risk of stroke (3). Sudden cardiac death, most often a result of ventricular arrhythmia (VA), accounts for 30-50% of the deaths in heart failure patients (4-5). CCM is a novel therapy for patients with heart failure with a variety of short and long-term benefits. While CCM has been shown to improve health status and reduce hospitalization rates in those with AF (6), there is a paucity of data examining the impact of CCM therapy on arrhythmia burden.

3 – Rationale, Objectives and Hypothesis

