5.3.2 Statistical Methods for Exploratory Objectives

All exploratory objectives will be performed for both retrospective and prospective arms separately and together with comparisons to be made between the following groups:

1. 6 months pre Optimizer to 6 post Optimizer months (post Optimizer months 3-8), after 2 month blanking period
2. 6 months pre Optimizer to 6 post Optimizer months (post Optimizer months 1-6)
3. 3 months pre Optimizer to 3 post Optimizer months (post Optimizer months 3-5), after 2 month blanking period
4. 3 months pre Optimizer to 3 post Optimizer months (post Optimizer months 6-8), after 2 month blanking period
5. 3 months pre Optimizer to 3 post Optimizer months (post Optimizer months 1-3)
6. 3 months pre Optimizer to 3 post Optimizer months (post Optimizer months 4-6)

Exploratory objective one is to compare the AF burden between groups 2-6 noted above.

Exploratory objective two is to compare the number of VA episodes between all groups noted above.

Exploratory objective three is to compare the AF burden after censoring subjects who underwent cardioversion or catheter ablation of AF during entire study period between all groups noted above.

Exploratory objective four is to compare the AF burden after censoring subjects who had addition of antiarrhythmic drug, underwent cardioversion, or underwent catheter ablation during entire study period between all groups noted above.

Exploratory objective five is to compare the number of hospitalizations between all groups noted above.

Exploratory objective six is to compare the number of stroke events between all groups noted above.

| | |
|--------------|------------|
| Study Number | 12/20/2022 |
|--------------|------------|

Exploratory objective seven is to compare the number of catheter ablations between all groups noted above.

Exploratory objective eight is to compare the number of cardioversions between all groups noted above.

Exploratory objective nine is to compare the number of AF events ≥ 24 hours between all groups noted above.

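### Death is not recorded and four event counts have no time denominator, so post-implant windows cut short by death or dropout lower the counts with no device effect

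*Combined protocol and SAP*

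**What the plan says.** Section 4.3 sets out what is collected besides device data: "Demographics, development of medical events (hospitalization, stroke) and arrhythmia related history (presence/absence of medications) and interventions". The examples of interventions given there are ablation, cardioversion and antiarrhythmic drugs. Death is not in that list, in the primary objective, in any of the nine exploratory objectives, or in the statistical methods. The missing-data allowance in 5.1 gives dropout and unavailable device data as its examples.

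Section 5.3.2 words four objectives as counts. For hospitalizations it reads: "Exploratory objective five is to compare the number of hospitalizations between all groups noted above". Objectives six, seven and eight use the same form of words for strokes, ablations and cardioversions.

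It then gives methods for two kinds of outcome only. AF burden is time in AF divided by follow-up time in the window. VA episodes are tabulated, and a Poisson GEE on the rate may be run. Objectives five to eight have no test, offset or denominator.

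Section 5.2 states: "All patients identified and enrolled will be included in the analyses". A patient who dies after implant therefore stays in the analysis.

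**The concern.** The two windows are not exposed to death in the same way. A patient must be alive at implant, so the six pre-implant months are always fully lived. The post-implant months need not be. If counts are compared as worded, a patient who dies in month 3 contributes six months of pre-implant events and only the events of a short post-implant period. The difference looks like improvement.

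Hospitalization, stroke and VA are the outcomes that a reader would look to for safety, and loss of follow-up moves their counts in the device's favour. Because death is not a data item, nothing in the report would show that this had happened. Section 5.4 applies the same methods at interim analyses after every 25 patients, and 6.6 allows interim results to be published, so favourable counts could appear with no deaths beside them.

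**Working it through.** **Figures in the plan.** The plan's own calculated figure is the 77 patients of 5.1. A paired t-test with mean change 5, SD 15, two-sided alpha 0.05 and power 0.8 needs 73. Dividing by the Wilcoxon efficiency 3/π gives 73 × π/3 = 76.4, so 77. It reproduces, and this point does not affect it. From 5.1 I use only the planned 92 patients per arm.

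**Where truncation by death can occur.**
- Prospective arm: yes, over all 8 months.
- Retrospective criterion b in 4.2.2 (under 8 months of follow-up, consent required): yes, but only after consent, because the patient has survived to that date.
- Retrospective criterion a (at least 8 months of follow-up): no. The main windows are complete by definition.

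**Assumed mortality.** The documents give no death rate. I assume 8-month mortality m of 3% to 10%. Annual rates of 5% and 15% give 1 − 0.95^(8/12) = 3.4% and 1 − 0.85^(8/12) = 10.3%. Among 92 prospective patients, 3-10% is 92 × 0.03 = 2.8 to 92 × 0.10 = 9.2 deaths.

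**Exposure lost in months 3-8.** Spread deaths evenly over 8 months. A death in the first two months (probability 2/8 = 0.25) loses all 6 months. A later death (0.75) loses 3 on average. The mean loss is 0.25 × 6 + 0.75 × 3 = 3.75 months per death. The share of exposure lost is m × 3.75/6, which is 1.9% at m = 3% and 6.3% at m = 10%.

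**Check with a constant death hazard.** Let λ = −ln(1 − m)/8. With no device effect and an unchanged event rate while alive, the expected post/pre count ratio is (e^(−2λ) − e^(−8λ))/(6λ).
- m = 5%: 0.969
- m = 10%: λ = 0.01317, ratio 0.937

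For months 6-8 alone, where truncation is heaviest, the ratios are 0.959 and 0.918.

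**If those who die have more events.** Suppose their event rate is three times that of survivors (an assumption). At m = 10%, in survivor-rate units per patient, survivors contribute 6 × 0.9 = 5.4 in each window. Those who die contribute 6 × 0.1 × 3 = 1.8 before implant. In months 3-8 they live 6 × 0.9365 − 5.4 = 0.219 patient-months, which is 0.657 after tripling. The ratio is (5.4 + 0.657)/(5.4 + 1.8) = 0.841. At m = 5% it is 0.914.

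**Effect on a test.** The plan names no test for these counts, so this is only an illustration. It is a simulation of a paired z-test on raw counts in 92 patients, at an assumed 0.5 events per patient per 6 months. With no deaths, a significant false reduction occurs in about 2.5% of trials. At m = 10% it occurs in 5.4%, or in 12.3% with the threefold rate.

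**What a denominator repairs.** With equal event rates, dividing by observed time restores a ratio of 1.0. With the threefold rate at m = 10%, pooled rates are 7.2/6 = 1.200 before and 6.057/5.619 = 1.078 after, a ratio of 0.898. That is closer to 1 than 0.841 but not equal to it, because higher-rate patients leave. Comparing rates within each patient gives 1.0 under these assumptions.

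**The case against.** The strongest reply is that the plan never says months after death count as zero events, and it does not forbid rates. That is correct: the raw-count reading follows from the words used and from the absence of any stated method. The alternative of dropping patients with incomplete windows conflicts with 5.2, and it would still leave the deaths unreported.

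Much is already protected. The primary AF burden is divided by follow-up time. AF episodes of at least 24 hours are reported per one-month period under 4.1 and 4.3. Patients with expected survival under one year are excluded, which should lower mortality. Retrospective patients with complete follow-up are unaffected. All of this stands and limits the point to a few exploratory objectives in part of the cohort.

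Three stronger readings are tempting, and the documents do not support them.
- A reader might infer that a fatal VA leaves no trace anywhere. VT or VF treated by an ICD is counted as a VA episode, and a fatal stroke or a death in hospital can count once under objectives five or six. The gap is a death with none of these. Such deaths are possible because 4.2.3 admits pacemaker patients and the VA categories contain no untreated sustained VT or VF.
- A reader might multiply assumed deaths by the background statement "Sudden cardiac death, most often a result of ventricular arrhythmia (VA), accounts for 30-50% of the deaths in heart failure patients" to count unrecorded sudden deaths. That share is for heart failure patients generally, not for a cohort carrying devices, and some such deaths would be counted.
- A reader might apply the bias to every patient in both arms. Criterion a of the retrospective arm rules that out, so I give no pooled error rate.

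**Conclusion.** The point holds for VA counts (objective two, when not analysed as a rate) and for objectives five to eight, in the prospective arm and in retrospective patients enrolled with under 8 months of follow-up. As worded, these comparisons favour the post-implant period whenever death or dropout shortens the window, and the plan collects no deaths that would reveal it.

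The size is modest: about 2-6% of months 3-8 exposure in the prospective arm at an assumed 8-month mortality of 3-10%. The fall in counts reaches about 9% at 5% mortality and 16% at 10% if those who die are assumed to have three times the event rate. Mortality and the threefold rate are assumptions. The direction follows from the design, given that counts are compared as worded. The primary AF burden measure does not have this count bias. The change should be made because it is cheap and because hospitalization, stroke and VA counts should not be read without the deaths.

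**What to change.** **Section 4.3.** Record death (date, and cause as available in the record) and the date observation ended for each patient, with the reason.

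**Section 5.3.2.** Analyse objectives two and five to eight as events per patient-month observed in each window, for example by a Poisson GEE with log observed time as offset. Make the VA rate model definite rather than optional. State that a patient with no observed time in a window contributes no record for it. A within-patient (conditional) Poisson analysis is a useful sensitivity check, because the offset alone does not remove the effect of higher-risk patients leaving.

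**Sections 5.3.2 and 5.4.** Report the number and timing of deaths since implant beside each of these comparisons, at interim and final analysis. Say in 5.4 whether a patient who has died counts as having complete data.

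**Cost.** A few REDCap fields, one paragraph of methods, some site effort to find dates and causes across up to 50 subsites, and possibly less favourable counts. Eligibility, sample size and the primary analysis do not change.
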